3.6.1.7 Objective Response Rate (ORR)

For Part 2, ORR will be calculated as the ratio of the number of participants reported to have achieved a confirmed CR or PR, divided by the number of participants in Part 2. Part 2 participants without ORR assessments will be counted as non-responders.

The point estimate of ORR will be provided, together with 95% CI using exact binomial method proposed by Clopper and Pearson (1934) [5].

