### 1.3.3 Imaging Schedule

	Imaging On Treatment	End of Treatment (EOT)	In Follow-up
Part 1 • Stage IIB and IIC • No evidence of disease at study entry	Every 6 months for one year from randomization	If previous imaging was obtained within 4 weeks prior to the date of discontinuation, imaging at treatment discontinuation is not mandatory.	
 
• Every 6 months in years 2-4 from randomization
 
• Once in year 5 from randomization
 

Part 2 • Stage III • No evidence of disease at entry into Part 2 after loco-regional recurrence	Every 12 weeks for one year from C1D1		
 
• Every 12 weeks in year 2 from C1D1
 
• Every 6 months from years 3-5 from C1D1
 
• Yearly thereafter
 

Part 2 • Stage IV • No evidence of disease at entry into Part 2 after distant recurrence	Every 12 weeks for one year from C1D1		
 
• Every 12 weeks in year 2 from C1D1 *
 
• Every 6 months from years 3-5 from C1D1
 
• Yearly thereafter
 

Part 2 • Stage III/IV • Have unresectable disease at entry into Part 2	Every 12 weeks for two years from C1D1		
 
• Every 12 weeks in year 3 from C1D1
 
• Every 6 months for years 4-5 from C1D1
 
• Yearly thereafter
 

C1D1= Cycle 1 Day 1 of Part 2 Treatment

Note: For participants who stop Part 1 or Part 2 without documented recurrence/progression. Every effort should be made to capture imaging based on Part 1 and Part 2 SoA instructions.

\* Participants who enter Part 2 with history of Stage IV melanoma and have no evidence of disease may be treated for up to 35 cycles and will have year 2 of imaging while on treatment.

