Participants will be stratified in Part 1 as follows: one stratum for pediatric participants ( $\geq 12$  years of age and  $< 18$  years of age) and 3 strata for adult participants ( $\geq 18$  years of age) based on T-stage tumor thickness and ulceration (T3b, T4a, T4b). In Part 1, study treatment must begin within 12 weeks of complete surgical resection. PK/antidrug antibody (ADA) data will be collected during Part 1 for pediatric participants. Disease recurrence is confirmed by investigator radiographically and/or by exam/biopsy and confirmed by the site via pathology. All participants will be unblinded after Sponsor consultation and approval at recurrence prior to crossover/rechallenge.

In Part 2, participants may receive up to 17 cycles or 35 cycles of pembrolizumab as adjuvant therapy per Part 2 eligibility guidelines (Section 6.7). Participants will receive 17 cycles of pembrolizumab Q3W after resection of recurrent disease if feasible (local recurrence, including local metastatic lymph nodes, or distant metastasis). Participants will receive up to 35 cycles Q3W for unresectable disease recurrence [unresectable local (regional metastatic lymph nodes, in-transit, satellite, and/or microsatellite metastases) or unresectable distant recurrence]. Participants with distant metastasis who undergo complete resection should receive 17 cycles but with Sponsor approval may receive 35 cycles. Participants who achieve a complete response (CR) per RECIST 1.1 may discontinue pembrolizumab after at least 8 administrations of treatment, including 2 doses beyond the date when the initial CR was declared. Participants receiving 35 cycles of therapy in Part 2 with partial response (PR) or stable disease (SD) per RECIST 1.1 or iPR or iSD per iRECIST should complete all 35

cycles of therapy. Participants are not eligible for further treatment with pembrolizumab beyond 35 cycles within the confines of the study. Participants will not be treated beyond true progression confirmed by iRECIST (see Section 8.2.1.6 for additional details).

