The imaging schedule for participants with local, surgically resected recurrence will be every 12 weeks during treatment. Investigators will assess recurrence radiographically (with site radiologist) and/or by examination with subsequent biopsy during treatment and follow-up. Lesions identified by physical examination should be photographed and submitted to the imaging vendor. For participants with unresectable local (regional metastatic lymph nodes, in-transit, satellite, and/or micrometastases) or distant recurrence imaging will also be every 12 weeks during treatment. Investigators will use RECIST 1.1/iRECIST to assess disease response/progression for participants entering Part 2 therapy with unresectable/metastatic disease.

Follow-up visits and imaging schedules will be scheduled in Part 1 and Part 2 per the SoA (Section 1.3).

Detailed information on Parts 1 and 2 is found in Section 8.

The primary endpoint of the study is RFS. Secondary endpoints include DMFS and OS. Distant metastasis refers to cancer that has spread from the original (primary) tumor and beyond local or nearby tissues and lymph nodes to distant organs or distant lymph nodes. This study will also examine the safety and tolerability of adult or pediatric pembrolizumab doses administered every 3 weeks for 17 cycles and at recurrence for 17 or 35 cycles as a secondary endpoint. Safety evaluations will include AE monitoring, physical examinations, clinical laboratory parameters (hematology and chemistry), vital signs, and assessment of ECOG, KPS or LPS (Appendix 8: Performance Status Scales). Adverse events will be monitored throughout the study and graded in severity according to the guidelines outlined in the NCI CTCAE Version 4.0.

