### **6.7 Part 2 – Crossover or Rechallenge Treatment After Recurrence**

The primary goal of the overall study is to compare RFS of pembrolizumab versus placebo, while ensuring access to pembrolizumab for all participants entering the study by allowing crossover/rechallenge after recurrence.

All participants will be unblinded at recurrence (Section 8.1.11) after Sponsor consultation and approval. The site should ensure data for disease recurrence is entered in the database prior to unblinding. Additionally, any AEs and/or SAEs should be reported and causality attributed in the database prior to unblinding. Participants will be encouraged to undergo full resection of the new lesion(s) if they experience local recurrence or have a biopsy if they experience unresectable or metastatic disease. Lymph node dissection should be undertaken per the recommendations of treating physician and surgeon.

For participants who decide to go on to Part 2 and otherwise meet criteria for crossover or rechallenge, resection or biopsy of unresectable or metastatic disease will be mandatory to confirm diagnosis. If biopsy is clinically contraindicated investigators should seek Sponsor review to start participant on Part 2 therapy. Participants should start Part 2 therapy within 4 weeks of recurrence. If participant requires longer time from surgical resection (eg, for recovery from surgery), Sponsor may be consulted to allow additional time before start of Part 2 therapy.

All participants who complete Part 1 study treatment with pembrolizumab or received placebo will be eligible for additional cycles of pembrolizumab if they meet Part 2 enrollment criteria listed below. Rechallenge/crossover is optional and is at the discretion of the Investigator upon notification of the Sponsor.

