Participants assigned in the Part 1 initial treatment phase to the placebo arm who experience recurrence at any point during Part 1 therapy and follow-up and meet all crossover criteria will be offered crossover to pembrolizumab per dosing criteria in Section 4.3. Participants on the pembrolizumab arm during the initial phase of treatment who are greater than 6 months from last dose of pembrolizumab treatment and who experience a recurrence will be offered rechallenge with pembrolizumab per dosing criteria outlined in Section 4.3. Participants who have local recurrence, including local metastatic lymph nodes or distant metastases that are surgically resected may receive up to 17 cycles of therapy with pembrolizumab and participants with an unresectable local (regional metastatic lymph nodes, in-transit, satellite, and/or microsatellite metastases) or an unresectable distant recurrence may receive up to 35 cycles of therapy with pembrolizumab per Section 1.3.2.

All participants should have screening imaging within 28 days prior to C1D1 in Part 2 Crossover/Rechallenge phase. The Part 1 EOT scan can be used as baseline for Part 2 if done within 4 weeks of 1st dose in Part 2. Participants who have had surgical resection of lesion

captured on imaging must have a scan after surgery or radiation is complete to establish baseline imaging within 4 weeks prior to start of Part 2 therapy. Brain MRI must be obtained within 4 weeks prior to start of Part 2 treatment, unless contradicted; then CT may be acquired.

Disease recurrence/progression is confirmed by investigator (radiographically and/or by exam with subsequent biopsy) and RECIST 1.1/iRECIST will be used to identify disease progression in participants with metastatic/unresectable disease identified at the start of Part 2 therapy. Local recurrence should be documented with photo image.

Radiotherapy (palliative or adjuvant) is allowed prior to Part 2 (eg, post lymph node dissection radiotherapy when indicated). Radiotherapy has to be completed prior to first dose and complete wound healing is required prior to first dose. Radiotherapy is allowed during treatment in Part 2 as palliative therapy (treatment of pain, impending fracture, etc.) in participants with unresectable recurrence or metastatic disease. If surgery or radiotherapy other than described above is indicated while on Part 2 therapy Sponsor must be consulted.

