All eligibility criteria from Part 1 Sections 5.1 and 5.2 remain valid and must be reconfirmed prior to enrollment into Part 2 of the study with the EXCEPTION of:

- Inclusion Criteria 2, 3, 4 and 5
- Exclusion Criteria 5, 6 and 11

Participants must also meet the following requirements for entry into Part 2:

- Participant must have experienced an investigator determined/confirmed disease recurrence radiographically and/or by exam with subsequent biopsy. Local recurrence must be documented with photo image. Participants will only be eligible for Part 2 treatment after the first recurrence. If a participant experiences a second recurrence, they will not be eligible for Part 2. Participants who are less than 6 months from their last Part 1 pembrolizumab dose at the time of recurrence are not eligible for Part 2 treatment.

Note: Cutaneous lesions and other superficial lesions detectable only by physical exam must be categorized as nontarget lesions for Part 2 of the study.

- No new anticancer treatment was administered after the last dose of Part 1 study treatment.
- Participant is continuing from Part 1 and has completed 17 cycles of pembrolizumab or any number of cycles with placebo with no delays in treatment  $\geq 12$  weeks. If a  $\geq 12$ -week treatment delay has occurred, Sponsor approval must be obtained before moving into Part 2 of the study.

Note: For any participant who is not able to complete the required 17 cycles of pembrolizumab or have  $\geq 12$ -week treatment delay on placebo arm, a notification to the Sponsor is required to determine if it would impact their eligibility for entry into Part 2.

- Surgical resection or biopsy of unresectable or metastatic disease completed within 4 weeks of first dose.

- Full resection of lesions or biopsy of unresectable or metastatic disease confirmed by site pathologist to be melanoma.

Note: If biopsy is clinically contraindicated, investigators should seek Sponsor review and approval to start participant on Part 2 therapy.

If participant is identified to have a thoracic lesion or lymph node suspicious for a recurrence (especially if solitary lesion), it is encouraged that a biopsy be performed to confirm metastatic melanoma versus another lung primary malignancy versus a nonmalignant lung disease (eg, sarcoidosis).

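### Part 2 ORR is divided by everyone in Part 2, including participants resected to no evidence of disease who cannot have a CR or PR, so this exploratory response rate is diluted

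*SAP*

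**What the plan says.** SAP section 3.6.1.7 takes the participants with a confirmed CR or PR, "divided by the number of participants in Part 2. Part 2 participants without ORR assessments will be counted as non-responders", and attaches an exact Clopper-Pearson 95% interval. Section 3.4.1.4 defines ORR over the analysis population. Section 3.5.1 sets the Part 2 efficacy population as those eligible under Protocol section 6.7. Section 3.6.1 states that Part 2 efficacy is summarised descriptively, separately by Part 1 randomised arm.

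The protocol places two kinds of participant in Part 2:

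- **Resected participants.** Section 4.1: "Participants will receive 17 cycles of pembrolizumab Q3W after resection of recurrent disease if feasible". Section 6.7 includes "distant metastases that are surgically resected may receive up to 17 cycles of therapy with pembrolizumab", and for local recurrence adds "Participants will be encouraged to undergo full resection of the new lesion(s) if they experience local recurrence". The imaging schedule in section 1.3.3 has a separate row for Stage III participants with "No evidence of disease at entry into Part 2 after loco-regional recurrence" and a matching row for Stage IV after distant recurrence.
- **Participants with disease at entry.** Section 4.1: "Investigators will use RECIST 1.1/iRECIST to assess disease response/progression for participants entering Part 2 therapy with unresectable/metastatic disease".

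Entry differs by Part 1 arm (section 6.7). Placebo participants "who experience recurrence at any point during Part 1 therapy and follow-up and meet all crossover criteria will be offered crossover to pembrolizumab". Pembrolizumab participants "less than 6 months from their last Part 1 pembrolizumab dose at the time of recurrence are not eligible for Part 2 treatment".

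**The concern.** A response rate is meaningful only among people who have something that can respond. A participant who starts Part 2 with no lesions cannot have a PR, because there is no tumour burden to shrink, and cannot have a CR, because there is nothing to disappear. For that participant a response assessment is inapplicable, not missing. The SAP rule treats the two situations alike and scores both as non-response.

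At stake is the reading of one descriptive result. A low Part 2 ORR could mean that pembrolizumab rarely produced responses after recurrence, or only that many recurrences had been resected before Part 2 began. The figure as defined cannot separate the two. Because results are shown by Part 1 arm and entry rules differ by arm, the NED share need not be the same in the crossover and rechallenge groups, and the two ORRs could differ for that reason alone.

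**Working it through.** **Step 1: is the denominator limited anywhere?** Section 3.6.1.7 uses all participants in Part 2. Section 3.4.1.4 defers to the analysis population. Section 3.5.1 defines that population by eligibility under Protocol section 6.7, whose criteria are met by full resection as well as by biopsy of unresectable or metastatic disease. None of these sections requires disease at Part 2 baseline, so NED participants are in the denominator.

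**Step 2: can they be in the numerator?** Protocol section 4.1 ties RECIST 1.1/iRECIST to participants entering with unresectable or metastatic disease. In Appendix 9, iPR depends on the sum of target-lesion diameters and iCR requires all lesions to resolve. With no lesions at baseline, neither can be reached. This is an inference from the criteria, not a sentence in the plan.

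**Step 3: the formula.** Let f be the share of Part 2 participants who are NED at entry and p the ORR among those with disease at entry. Then

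reported ORR = p × (1 − f) + 0 × f = p × (1 − f).

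The largest possible value is 1 − f, reached if every participant with disease responds.

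**Step 4: illustration.** The plan gives no expected Part 2 ORR, Part 2 sample size or NED share, so there is no figure to reproduce. Assumed here: p = 40%, and 100 Part 2 participants in one Part 1 arm. Intervals are exact Clopper-Pearson 95%.

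| NED share f | p × (1 − f) | SAP rule | Disease at entry only |
|---|---|---|---|
| 30% | 0.40 × 0.70 | 28/100 = 28% (19.5 to 37.9) | 28/70 = 40% (28.5 to 52.4) |
| 50% | 0.40 × 0.50 | 20/100 = 20% (12.7 to 29.2) | 20/50 = 40% (26.4 to 54.8) |
| 70% | 0.40 × 0.30 | 12/100 = 12% (6.4 to 20.0) | 12/30 = 40% (22.7 to 59.4) |

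**Step 5: dependence on the assumptions.** The dilution of the point estimate does not depend on the number of participants. Whether the interval still covers p does. At n = 100 all three SAP-rule intervals exclude 40%. At f = 30%, 14/50 gives 16.2 to 42.5 and 7/25 gives 12.1 to 49.4. At f = 50%, 5/25 gives 6.8 to 40.7. Those three contain 40%.

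**Step 6: by Part 1 arm.** If p were 40% in both arms but f were 25% in one and 75% in the other (assumed), the reported ORRs would be 0.40 × 0.75 = 30% and 0.40 × 0.25 = 10%.

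**The case against.** The strongest reply concerns weight. Part 2 ORR is not among the protocol or SAP objectives. It is exploratory, purely descriptive and outside the alpha scheme, and no planned decision uses it. That stands and is why the point ranks low.

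Other replies, and what remains of them:

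- **The quantity is well defined.** It is the proportion of all Part 2 participants with a confirmed response, and counting missing as non-response is a sound conservative convention. Both are true, but the convention is conservative only for people who could respond. Labelled as an ORR, the figure will be read as a response rate among people with disease, which it is not.
- **The plan does not say that RECIST applies only to participants with disease.** Correct. Protocol section 8.2.1.2 says without restriction that Part 2 response is based on RECIST 1.1/iRECIST. This does not help, because participants with no lesions still have no route to CR or PR.
- **Intervals that exclude 40% depend on n = 100.** This stands, as step 5 shows. The point-estimate dilution is unaffected.
- **The arms are not comparable anyway.** This also stands. Crossover and rechallenge participants are selected after randomisation and differ in prior exposure. No comparison of their ORRs is planned. A corrected denominator removes the NED-share component but does not make the arms comparable.

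**Conclusion.** The concern holds. As written, the Part 2 ORR includes in its denominator participants who cannot respond. It is biased downward as a response rate whenever at least one NED participant enters and at least one participant with disease responds, and it is capped at one minus the NED share. Encouraged resection and dedicated NED imaging groups make such participants an expected part of Part 2.

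The direction follows from the documents. The size does not: the reported 28%, 20% and 12% against 40% rest on the assumed response rate and NED shares, and the intervals also on the assumed 100 participants. The consequence is confined to one exploratory, descriptive result. The change should be made before that result is reported, but it does not touch RFS, DMFS, OS or type I error.

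**What to change.** In SAP section 3.6.1.7, with a matching sentence for ORR in section 3.5.1:

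1. Define the ORR denominator as participants who received at least one Part 2 dose and had unresectable or residual disease at Part 2 baseline. The dosing condition agrees with section 3.4.1.4, where Part 2 PFS and OS start at the first Part 2 dose.
2. Do not require measurable disease. Protocol section 6.7 makes brain lesions, and superficial lesions found only on examination, nontarget; participants with only such lesions still have disease that can be assessed.
3. Count a missing assessment as non-response within this set only.
4. Report, by Part 1 arm, how many NED participants fall outside it. The all-Part 2 proportion may be kept as a secondary line if clearly labelled.
5. Optionally, show Part 2 PFS separately for those with disease and those with NED at entry. Duration of response needs no change, because section 3.6.1.8 is already limited to confirmed responders.

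The cost is SAP wording. The resection outcome of the first recurrence is already needed to derive PRFS2 and to assign the Part 2 imaging schedule, so no new data item should be required. The interval becomes wider: in the assumed 50% NED case, 54.8 − 26.4 = 28.4 points on 50 participants, against 29.2 − 12.7 = 16.5 points on 100. The wider interval is the precision actually available on the response rate.

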3.6.1.8 Duration of Response (DOR)

If sample size permits, DOR will be summarized descriptively using Kaplan-Meier medians and quartiles. Only the subset of Part 2 participants who show a confirmed complete response or partial response will be included in this analysis. Censoring rules for DOR are summarized in [Table 3](#).

For each DOR analysis, a corresponding summary of the reasons responding participants are censored will also be provided. Responding participants who are alive, have not progressed, have not initiated new anti-cancer treatment, have not been determined to be lost to follow-up, and have had a disease assessment within ~6 months of the data cutoff date are considered ongoing responders at the time of analysis. If a subject meets multiple criteria for censoring, the censoring criterion that occurs earliest will be applied.

Table 3 Censoring Rules for DOR

Situation	Date of Progression or Censoring	Outcome
No progression nor death, no new anticancer therapy initiated	Last adequate disease assessment	Censor (non-event)
No progression nor death, new anticancer therapy initiated	Last adequate disease assessment before new anti-cancer therapy initiated	Censor (non-event)
Death or progression immediately after ≥ 2 consecutive missed disease assessments or after new anti-cancer therapy, if any	Earlier date of last adequate disease assessment prior to ≥ 2 missed adequate disease assessments and new anti-cancer therapy, if any	Censor (non-event)
Death or progression after ≤ 1 missed disease assessments and before new anti-cancer therapy, if any	PD or death	End of response (Event)
Note: A missed disease assessment includes any assessment that is not obtained or is considered inadequate for evaluation of response.		

3.6.1.9 Analysis Strategy for Key Efficacy Endpoints

Table 4 summarizes the primary analysis approach for primary and key secondary efficacy endpoints. Sensitivity analysis methods are described above for each endpoint as applicable.

Table 4 Efficacy Analysis Methods for Key Efficacy Endpoints

Endpoint/Variable (Description, Time Point)	Statistical Method [†]	Analysis Population	Missing Data Approach
Primary Hypothesis 1			
RFS	Test: Stratified log-rank test Estimation: Stratified Cox model with Efron's tie handling method	ITT	See Table 1 for censoring rules
Secondary Hypothesis 2			
DMFS	Test: Stratified log-rank test Estimation: Stratified Cox model with Efron's tie handling method	ITT	Censored at last disease evaluation
Secondary Hypothesis 3			
OS	Test: Stratified log-rank test Estimation: Stratified Cox model with Efron's tie handling method	ITT	Censored at last known alive date
[†] Statistical models are described in further details in the text. For stratified analyses, the stratification factors used for randomization will be used as stratification factors for analysis.			

